## STUDY SYNOPSIS

Sponsor / Sponsor-Investigator	University Hospitals of Geneva / [name]
Study Title:	Harnessing the beneficial non-specific effects of measles-mumps-rubella vaccine on infection with unrelated pathogens and allergic diseases in children – a single-centre phase IV randomised controlled trial with a factorial design comparing the current Swiss vaccination schedule with a modified schedule
Short Title / Study ID:	Non-specific Effects of a modified Measles vaccination schedule to prevent Allergy and Unrelated infection in children (NEMAU) 2022-00616
Protocol Version and Date:	1.2 08.03.2023
Trial registration:	Clinicaltrial.gov NCT05758532
Study category and Rationale	A (licenced vaccine, used in accordance with recommendation)
Clinical Phase:	Phase IV (licenced vaccine, within recommendation, evaluated for beneficial effect beyond the initial scope of approval)
Background and Rationale:	
In addition to their specific effect against the target disease, some vaccines induce broader changes to immune function, resulting in “non-specific effects”. Evidence suggests that measles vaccines can protect against unrelated infections and reduce all-cause mortality by as much as half in infants. In two trials in Guinea-Bissau, an early dose of measles vaccine (before 9 months of age) was associated with reduced risk of hospital admission and of mild infections in the months following vaccination. Importantly, the non-specific effects are mainly observed when the measles-containing vaccine (such as the measles-mumps-rubella (MMR) vaccine) is not given concomitantly with non-live vaccines. Measles vaccination has also been associated with a reduced risk of allergy in children. The immunological mechanisms underlying the non-specific effects of the measles vaccine have not been investigated, despite this vaccine being given almost universally to children.
 
The overall objective of this project is to assess, in a randomised control trial (RCT), the effects of a “modified” MMR schedule in children, by an in-depth characterisation of both the clinical effects and the underlying immunomodulatory changes. The current Swiss administration schedule of giving MMR at 9 and 12 months of age (“current schedule”) will be compared with a “modified schedule”. This is expected to maximise the beneficial non-specific effects of MMR by giving it at 6 and 13 months of age, separately from other vaccines (“modified schedule”). Factorial analysis will enable assessment of the benefit of the intervention on each of the two doses of MMR separately or in combination.

Objective(s):	The clinical aims are to determine whether a modified schedule of MMR administration reduces both the risk and severity of: (i) infections with unrelated pathogens and (ii) atopic and allergic diseases. The laboratory aims are to: (i) quantify and characterise the immunological non-specific effects of MMR, and (ii) identify the biological pathways and molecular mechanisms that are altered by MMR vaccination.

Outcome(s):	
Primary outcome: Number of parent-reported respiratory infections between 6 months and 9 months of age.
 
Main secondary outcomes:
 
 
• Additional measures of infection
 
• Eczema, food allergy, and wheezing diseases
 
• Immune cell sub-populations and function over time
 
• Transcriptional responses and epigenetic imprinting in immune cells
 
• Vaccine responses and memory cells
 
• Vaccine safety
 
																														
Study design:	Phase IV, single-centre, 4-group, open-label, randomised controlled trial with a factorial design (primary outcome analysed as a 2-group trial)																														
Inclusion / Exclusion criteria:	6-month-old healthy children fully immunised with no contraindications to MMR and no indication for an early MMR or MMR-varicella vaccination																														
Measurements and procedures:	
Parents will be asked to complete questionnaires once every 2 weeks to collect clinical data. Consent to blood tests is optional, and will determine whether a child participates in Part 1 only, or both Part 1 and Part 2.
 
Visits are planned at
 
 
• 6 months of age (randomisation, ± vaccination, ± blood collection),
 
• 9 months of age (± vaccination, ± blood collection),
 
• 11 to 13 months of age (vaccination), and
 
• 24 months of age (± blood collection).
 
																														
Study Product / Intervention:	
Measles-mumps-rubella (MMR) vaccine (Priorix): 0.5 ml injected intramuscularly in the deltoid region or in the anterolateral area of the thigh
 
Administration schedule will differ between the 4 groups, as follow:
 
  
 	Age:	
 
 	6 m	9 m	11-12 m	13 m	
   
 Group C.C. (both MMR on Current schedule)	No vaccine	1st MMR	3rd DTP and PCV 2nd MMR	No vaccine	
 
 Group M.C. (1st MMR Modified schedule, 2nd MMR Current schedule)	1st MMR	No vaccine	3rd DTP and PCV 2nd MMR	No vaccine	
 
 Group C.M. (1st MMR Current schedule, 2nd MMR Modified schedule)	No vaccine	1st MMR	3rd DTP and PCV	2nd MMR	
 
 Group M.M. (both MMR on Modified schedule)	1st MMR	No vaccine	3rd DTP and PCV	2nd MMR	
  
 
C: current schedule; DTP: diphtheria-tetanus-pertussis-containing vaccine; m: months of age; M: modified schedule; PCV: pneumococcal conjugate vaccine.
		Age:					6 m	9 m	11-12 m	13 m	Group C.C. (both MMR on Current schedule)	No vaccine	1 st MMR	3 rd DTP and PCV 2 nd MMR	No vaccine	Group M.C. (1 st MMR Modified schedule, 2 nd MMR Current schedule)	1 st MMR	No vaccine	3 rd DTP and PCV 2 nd MMR	No vaccine	Group C.M. (1 st MMR Current schedule, 2 nd MMR Modified schedule)	No vaccine	1 st MMR	3 rd DTP and PCV	2 nd MMR	Group M.M. (both MMR on Modified schedule)	1 st MMR	No vaccine	3 rd DTP and PCV	2 nd MMR
	Age:																														
	6 m	9 m	11-12 m	13 m																											
Group C.C. (both MMR on Current schedule)	No vaccine	1 st MMR	3 rd DTP and PCV 2 nd MMR	No vaccine																											
Group M.C. (1 st MMR Modified schedule, 2 nd MMR Current schedule)	1 st MMR	No vaccine	3 rd DTP and PCV 2 nd MMR	No vaccine																											
Group C.M. (1 st MMR Current schedule, 2 nd MMR Modified schedule)	No vaccine	1 st MMR	3 rd DTP and PCV	2 nd MMR																											
Group M.M. (both MMR on Modified schedule)	1 st MMR	No vaccine	3 rd DTP and PCV	2 nd MMR																											
Control Intervention:	The interventional product given to the control group will be the same as for the intervention groups, but with a different schedule of administration (see table above).																														

Number of Participants with Rationale:	
500 participants randomised into 4 groups (125 per group).
 
Sample size is based on the primary outcome of respiratory infections. Based on the data from a previous trial, we expect a rate of respiratory infection of 0.29 episodes per month (SD 0.32) between 6 and 9 months of age in the control groups (Group C.M. or C.C.). By randomising 500 participants, we will have 80% power to detect a minimum of 30% reduction in this incidence with a 2-sided p-value of 0.05, assuming at least 85% completion rate of the 9 months questionnaire. The primary outcome will be analysed as a 2-group comparison: the 250 children receiving MMR at 6 months of age (Group M.C. or M.M.) will be compared with the 250 children receiving the MMR at 9 months of age (Group C.M. or C.C.).
 
Among the 500 participants enrolled, 100 participants consenting to blood collection (Part 2) will be randomised in a different strata within the 4 groups (25 per group). Assuming that at least 60% of them will provide a sufficient blood sample at each time point, which will then be processed without any problem, these 100 participants in total are required for Part 2, to ensure that a minimum of 30 participants per group of 1st MMR timing (30 in Group M.C. or M.M., and 30 in Group C.M. or C.C.) are included in all analyses. This will provide >80% power to detect a biologically significant 1.5-fold-change in cytokine responses at the 5% significance level, based on the variance of previous infant cytokine and intracellular cytokine staining studies.

Study Duration:	3 years


Statistical Considerations:
	
The full details of the analysis will be provided in the statistical analysis plan, which will be finalised prior to database lock.
 
The primary outcome (number of respiratory infections between 6 and 9 months of age) will be compared between the two groups of 1st MMR timing (Group M.C. and M.M. vs. Group C.M. and C.C.) using negative binomial regressions, adjusted for sex (male/female), day-care attendance (yes/no), presence of comorbidities (yes/no), older siblings (yes/no), and will be presented as adjusted incidence rate ratios (aIRRs) with 95% confidence intervals.
 
Other comparative analyses at the 9-months and 2-years endpoints will be done using chi-square test (or Fisher's test when appropriate) for categorical variables, and paired t-test or Wilcoxon signed-rank test for continuous variables, depending on the distribution of the variable. Time-to-event outcomes will be assessed using Cox proportional hazards with adjustment for baseline risk factors.
 
For the 2-years endpoints, factorial analysis will enable to measure the effect on all outcomes of the intervention made to the first and the second dose of MMR, separately or in combination.
 
Regression will be used to identify independent factors associated with each of the outcomes. All significant predictors (<math>p < 0.20</math>) will be then included in a stepwise backward multivariate analysis.
 
Trauma and accident outcomes will also be compared between the two groups and will act as control events, as MMR is not believed to change their risk of occurrence.
 
Subgroup analysis are planned (by sex, risk factor, underlying maternal immunity, etc.).
 
The analyses will be done in collaboration with the Clinical Research Center at Geneva University Hospitals.

GCP Statement:
	
This study will be conducted in compliance with the protocol, the current version of the Declaration of Helsinki, ICH-GCP, as well as all national legal and regulatory requirements.

## ABBREVIATIONS

AE	Adverse Event
BASEC	Business Administration System for Ethical Committees, ( https://submissions.swissethics.ch/en/ )
BCG	Bacille Calmette-Guérin
CA	Competent Authority (e.g. Swissmedic)
CCER	Geneva Cantonal Ethics Commission
CEC	Competent Ethics Committee
CI	Confidence interval
CRF	Case Report Form
ClinO	Ordinance on Clinical Trials in Human Research ( in German: KlinV, in French: Oclin, in Italian: OSRUm )
eCRF	Electronic Case Report Form
CTCAE	Common terminology criteria for adverse events
DSMB	Data and Safety Monitoring Board
DSUR	Development safety update report

DTP	Diphtheria-tetanus-pertussis-containing vaccine
GCP	Good Clinical Practice
Group C.C.	Receive both MMR on Current schedule
Group C.M.	Receive 1 st MMR on Current schedule and 2 nd MMR on Modified schedule
Group M.C.	Receive 1 st MMR on Modified schedule and 2 nd MMR on Current schedule
Group M.M.	Receive both MMR on Modified schedule
Ho	Null hypothesis
HRA	Federal Act on Research involving Human Beings ( in German: HFG, in French: LRH, in Italian: LRUm )
ICS	Intracellular cytokine staining
IFN- $\gamma$	Interferon-gamma
IMP	Investigational Medicinal Product
IIT	Investigator-initiated Trial
ITP	Idiopathic thrombocytopaenic purpura
ITT	Intention to treat
KOFAM	Coordination Office for Human Research ( in German: Koordinationsstelle Forschung am Menschen )
MIS BAIR	Melbourne Infant Study: BCG for Allergy and Infection Reduction
MMR	Measles-mumps-rubella vaccine
MMRV	Measles-mumps-rubella-varicella vaccine
PCV	Pneumococcal conjugate vaccine
PI	Principal Investigator
PICF	Participant informed consent form
RCT	Randomised controlled trial
SDV	Source Data Verification
SNSF	Swiss National Science Foundation
SOP	Standard Operating Procedure
SPC	Summary of product characteristics
SUSAR	Suspected Unexpected Serious Adverse Reaction
Th	T helper cell
TLR	Toll-like receptor
TMF	Trial Master File
WHO	World Health Organization

## SUMMARY OF THE REVISION HISTORY IN CASE OF AMENDMENTS

Version Nr, Version Date	Chapter	Description of change	Reason for the change
1.0, 24.03.2022		Initial release	
1.1, 06.05.2022, following CCER review	Many	Terminology: "optimised" schedule changed to "modified" schedule	The neutral term "modified" is more suitable, as the benefit of the alternate schedule is not proven yet
	3.1	Added precision on investigators' role	Requested by CCER
	7.4, 8.5, and 9.2.5	Added precision on participant follow- up If withdrawal is due to an AE	Requested by CCER
	9.2	Added precision on blood transport and analysis	Requested by CCER
1.2, 08.03.2023, protocol tidy up before the inclusion of the first participant	Title page, synopsis, 1.2, 2.1, 13, 14.1	Added the Clinicaltrial.gov and KOFAM registration numbers Updated PI phone number Updated planned start and completion dates Updated funding section	Update needed
	1.5	Change of monitoring institution Slight change in monitoring plan	Following advice from HUG's Clinical Trials Unit's monitoring unit
	2.7, 7.2, 9.3.1	Updated places for advertising the study	Following advice from the Communication Unit of HUG
	9.2	Added justification for collecting the participants' date of birth	Following advice from the CCER

## STUDY SCHEDULE

Visit number	V1		V2		V3 a		V4	
Time point	t 0	t 0 to t +3m	t +3m	t +3m to t +6m	t +6m	t +7m	t +6m to t +18m	t +18m
Age of participant	6mo	6mo to 9mo	9mo	9mo to 12mo	12mo	13mo	12mo to 24mo	24mo
Allowed time frame	±2w	±1w	±2w	±1w	±2w	±2w	±1w	±4w
Recruitment								
Screening, eligibility check	X							
Inclusion and randomisation	X							
Baseline questionnaire b	X							
Intervention: MMR vaccination								
- Control Group C.C.			X		X			
- Intervention Group M.C.	X				X			
- Intervention Group C.M.			X			X		
- Intervention Group M.M.	X					X		
Assessments								
Clinical assessment c	X		X		X			X
Clinical questionnaires		X...X...X...X d		X...X...X...X e			X...X...X...X e	
Vaccine diary (S/AE)		X f		X f			X f	
Contact with treating paediatrician	X		X		X			X
Health record check	X		X					X
Blood collection (Part 2 only)	X		X					X

C: current schedule; MMR: measles-mumps-rubella vaccination; m: month; M: modified schedule; mo: month-old; S/AE: (serious) adverse event; V: visit; w: week.

a Timing of V3 differs between groups: 13 mo for Group M.M. and Group C.M., and 12 mo for Group M.C and Group C.C. If funding is insufficient, V3 might be simplified and delegated to the treating paediatrician.

b Includes demographics, medical history.

c Includes physical examination and eczema assessment using SCORAD.

[figure not shown]
d every 2 weeks.

e every month.

f follow-up 42 days after vaccination.

		Stage B: comparison for the timing of the 2nd MMR		
		2 nd MMR 1m after the 12y DPT-PCV (Modified)	2 nd MMR concomitant with the 12y DPT-PCV (Current)	
Stage A: comparison for the timing of the 1st MMR	1 st MMR at 6m (Modified)	Group M.M. , n=125 (including 25 in Part 2)	Group M.C. , n=125 (including 25 in Part 2)	N=250 (including 50 in Part 2)
	1 st MMR at 9m (Current)	Group C.M. , n=125 (including 25 in Part 2)	Group C.C. , n=125 (including 25 in Part 2)	N=250 (including 50 in Part 2)
		N=250 (including 50 in Part 2)	N=250 (including 50 in Part 2)	

Participant allocation in 4 groups. C: current MMR schedule; DTP: diphtheria-tetanus-pertussis vaccine; m: month; M: Modified MMR schedule; PCV: pneumococcal conjugate vaccine.

Current Swiss administration schedule and Study flowchart

(see section 6.1.3)

## 1.5 Monitoring institution

Monitoring will be performed according to ICH Good Clinical Practice (GCP) by the HUG's Platform for Clinical Research in Paediatrics, Gynaecology and Obstetrics.

## 1.6 Data Safety Monitoring Committee

An independent Data and Safety Monitoring Board (DSMB) will be convened three times during the study: before the first recruitment and at 6 and 18 months after the first recruitment.

The DSMB will monitor safety, data completeness, and the general study conduct. All the details of the DSMB analyses will be outlined in the DSMB charter.

The DSMB will be composed of individuals with the appropriate expertise, including at least three independent clinicians and/or biostatisticians who, collectively, have experience in the management of biostatistics and the conduct and monitoring of randomised controlled trials. Members of the DSMB will be independent of trial conduct. The DSMB will provide its input to the Principal Investigator.

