### 6.4 Risk mitigation of the trial design

**Variability in infectious risk:** Individual risk of infection depends on host (predisposition) and environmental (exposure) factors. Randomisation should ensure that risk factors are equally distributed between the two groups. The risk of those factors influencing the outcomes is also addressed by adjusting the analyses by the presence of comorbidities (host predisposition), siblings and day-care attendance (environmental exposure).

**Recruitment:** Recruitment will be through a network of private paediatricians highly motivated in contributing to clinical research. Pamphlets will be distributed in maternity services and paediatricians' offices; infants will be recruited during the first few months of age and parents will have opportunity to ask questions before the randomisation visit at 6 months of age. With over 5000 live births per year in Geneva, a minimum acceptance rate of 5% for Part 1 (questionnaires only) and of 1% for blood testing will enable recruitment to be completed in 18 months.

**Study burden / acceptance of the study:** The online questionnaire is being designed in partnership with parents in order to make it as user-friendly as possible. It will be completed every 2 weeks by participants' parents on a smartphone, computer or tablet following a participant-specific link sent by text or email, and will take less than 10 minutes to complete. The questionnaire includes many fields per participant but, thanks to branching algorithms, only items relevant to each participant will be displayed (based on the answers to previous questions). This design reduces redundancy and reduces the risk of missing or duplicate data.

**Accuracy of parent-reported data:** The questionnaire uses pre-filled fields, drop-down menus, and other measures to reduce the time taken for completion, and to increase the accuracy of the data. The data will be reviewed with the treating paediatrician, and the parents during the clinic visit, to retrieve any missing information. The child's medical records will also be checked. Clinical assessment will take place during the study visit to confirm some of the outcomes (e.g. presence of eczema using validated scores).

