### 11.2 Determination of Sample Size

The sample size calculation for the clinical outcome (500 participants) is based on the primary outcome of respiratory infections. Based on the data from a previous trial, we expect a rate of respiratory infection of 0.29 episodes per month (SD 0.32) between 6 and 9 months of age in the control groups (Group C.M. or C.C.). By randomising 500 participants, we will have an 80% power to detect a minimum of 30% reduction in this incidence with a 2-sided p-value of 0.05, assuming at least 85% completion rate of the 9 months questionnaire. The 500 participants will be randomised into 4 groups of similar size (see Section 6 and table 3 in Section 8.1): for the primary outcome analysis, the 250 children receiving early MMR at 6 months of age (Group M.C. or M.M.) will be compared with the 250 children receiving the regular MMR at 9 months of age (Group C.M. or C.C.).

		Timing of the 2 nd MMR		
		2 nd MMR 1m after the 12y DPT-PCV (Modified)	2 nd MMR concomitant to the 12y DPT-PCV (Current)	
Primary outcome comparing the timing of the 1 st MMR	1 st MMR at 6m (Modified)	Group M.M., n=125	Group M.C., n=125	N=250
	1 st MMR at 9m (Current)	Group C.M., n=125	Group C.C., n=125	N=250
		N=250	N=250	

Table 7. Participant allocation in 4 groups; for the primary outcome analysis, the Groups M.C. and M.M. will be compared with the Groups C.M. and C.C. C: current MMR schedule; DTP: diphtheria-tetanus-pertussis vaccine; m: month; M: Modified MMR schedule; PCV: pneumococcal conjugate vaccine.

The sample size calculation for the laboratory outcomes (100 participants) is more conservative as it depends on the success of the blood collection and of the laboratory processing for each of the time points. The use of paired samples (taken from the same infant at different ages) reduces the effect of inter-individual heterogeneity and provides greater statistical power with lower participant numbers.

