#### 11.4.4 Interim analyses

An interim safety analysis will be performed after the first 250 subjects have been randomized and reached the 9-months-old visit; a safety report detailing the results of the analysis will be compiled for the DSMB and the CCER.

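### The interim safety report for the DSMB falls due at about month 12, between the board's fixed meetings at months 6 and 18, so on the planned accrual no convened review of it is scheduled while early MMR doses are still being given

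*Protocol*

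**What the plan says.** Protocol section 1.6 states that the DSMB "will be convened three times during the study", namely "before the first recruitment and at 6 and 18 months after the first recruitment". It gives the board the task of monitoring safety, data completeness and conduct, and leaves the details of the board's analyses to a charter. The number and timing of the meetings are set in the protocol itself.

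Section 11.4.4 works on a different clock: "An interim safety analysis will be performed after the first 250 subjects have been randomized and reached the 9-months-old visit". It adds that "a safety report detailing the results of the analysis will be compiled for the DSMB and the CCER". The CCER is the ethics committee.

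Section 6.4 says that the expected acceptance rates "will enable recruitment to be completed in 18 months". Under section 9.3.2 the early dose (groups M.C. and M.M.) is given at Visit 1, on randomisation. Nothing in the protocol links a DSMB meeting to the interim report or pauses recruitment for it.

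**The concern.** One schedule is set by the calendar and the other by enrolment, and the protocol does not say how they meet. The safety of MMR at 6 months is a stated objective (section 4.4, AIM10). A by-group safety report halfway through the trial is of most use to children not yet dosed if the board considers it while early doses are still being given. If the report arrives between two fixed meetings, and the later one coincides with the end of recruitment, the text schedules no convened discussion of it during that time. This holds even if recruitment runs exactly to plan.

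**Working it through.** **Inputs.** 500 randomised, 250 of them to the early dose (synopsis; section 11.2). Recruitment in 18 months (section 6.4). Visit 2 is 3 months after randomisation, within 2 weeks either way (section 9.3.3). Second MMR is given 6 months after randomisation in M.C. and C.C., and 7 months after in C.M. and M.M. (study schedule). The accrual shape is not stated; even accrual is assumed and then varied. No time is allowed for compiling the report.

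**The 18-month figure.** Section 6.4 cites over 5000 births a year and "a minimum acceptance rate of 5% for Part 1 (questionnaires only) and of 1% for blood testing". At exactly 5000 births:
- 5% + 1% = 6%: 300 a year, and 500/300 × 12 = 20 months.
- 5% alone: 250 a year, and 500/250 × 12 = 24 months.

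These inputs are lower bounds, so 18 months is attainable but does not follow from them. All three durations are carried forward.

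**Trigger on the 18-month plan.**
- Rate: 500/18 = 27.8 a month.
- 250th child randomised: 250/27.8 = month 9.0.
- That child's 9-month visit: 9.0 + 3 = month 12.0 (11.5 to 12.5 with the visit window).
- Randomised by then: 27.8 × 12 = 333.
- Early doses still to give: (500 − 333)/2 = about 83.

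**The two meetings.**
- Month 6: 27.8 × 6 = 167 randomised, so about 83 early doses given; 27.8 × 3 = 83 children are past the 9-month visit. For the report to be ready, 250 children would have to be randomised in the first 3 months.
- Month 18: 500 of 500 randomised, no early doses left, 6 months after the trigger.

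**Longer recruitment.**

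| Recruitment | Trigger | Randomised at month 18 | Early doses left at month 18 |
|---|---|---|---|
| 18 months | month 12 | 500 | 0 |
| 20 months | month 13 | 450 | 25 |
| 24 months | month 15 | 375 | about 62 |

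**Uneven accrual over 18 months.** With cumulative recruitment 500 × (t/18)^k and k from 0.7 to 3, the trigger moves from month 9.7 to month 17.3. It always lies between the two meetings. The early doses left at the trigger fall from about 88 to about 28 as accrual becomes more back-loaded.

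**Second doses on the 18-month plan.** At month t the number given is half of those randomised by t − 6 plus half of those randomised by t − 7.
- Month 12: (167 + 139)/2 = 153, leaving 347.
- Month 18: (333 + 306)/2 = about 319, leaving about 181.
- Month 21, when the last child reaches the 9-month visit and the primary analysis can start: (417 + 389)/2 = 403.

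**The case against.** The strongest reply is that this is a coordination gap and that oversight does not lapse. Several parts of that reply stand.

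- A reader might infer that the interim report can protect nobody. The protocol does not support this. Section 11.4.4 does not say that the report waits for a meeting, board members could read it when it is issued, and section 1.6 does not confine their input to meetings. The CCER also receives it and may end the study on safety grounds (section 2.9).
- A reader might infer that the board sees no early-dose safety data in time. The month-6 meeting can review about 83 early doses, with about two thirds of the 250 still to come. SAEs reach the sponsor-investigator within 24 hours (section 10.1.2.1).
- A reader might take the interim as the only by-group safety analysis. Section 11.4.5 plans three: at the interim, the primary and the final analysis. On the planned accrual only the interim falls during early dosing.
- A reader might conclude that all early doses are certain to be given before the board meets on the report. That depends on recruitment ending by month 18.
- The vaccine is licensed and section 3.7 rates the study as low risk.

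The charter is not at hand and may allow extra meetings. But section 1.6 leaves to it the details of the analyses; the three meetings and their dates are fixed in the protocol. What the reply does not remove is that no text tells the board when or how to consider a report addressed to it.

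**Conclusion.** The point holds as a mismatch between sections 1.6 and 11.4.4. On even accrual over 18 months, the interim report is triggered at about month 12, with about 83 of 250 early doses still to give, and the next convened meeting comes when none remain. At 20 to 24 months, about 25 to 62 would remain. The trigger fell between the two meetings in every scenario tested; the number of children affected depends on the assumed accrual. Time needed to compile the report would reduce the number who could benefit.

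The consequence is limited: a scheduled, convened review is missing when it would be most useful, while other safeguards continue. It should be corrected, but it is not a flaw that stops the trial. The second doses given after month 18 are not a separate defect, since the stated safety objective concerns the early dose; they matter here for the cost of the remedy.

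**What to change.** In sections 1.6 and 11.4.4, state that the DSMB reviews the 11.4.4 report and gives its recommendation within a stated number of weeks of the trigger. On even 18-month accrual about 14 early doses are given each month (27.8/2), which helps in choosing that number. There are two ways to do it:

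1. **Tie the third meeting to the report.** The number of meetings stays at three, but the date floats. On the planned accrual the last convened meeting moves to about month 12, so about 347 second doses follow it instead of about 181. To offset this in part, send the DSMB the section 11.4.5 safety analysis done at the primary analysis, at about month 21, when about 403 second doses will have been given.
2. **Keep month 18 and review the report by circulation or teleconference.** This costs one short extra review and leaves second-dose oversight unchanged.

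Either way the change is a sentence or two in the protocol, with the charter aligned to it. No dose, schedule or clinical rule is affected.
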